5.1.3 Treatment Extension Period (Week 12 to Week 48)

After completing the 12-week Treatment Period, subjects will enter a 36-week Treatment Extension Period and will receive the following treatments:

- Subjects randomized to bimekizumab during the Treatment Period will receive bimekizumab 320mg sc Q4W from Week 12 to Week 44.
- Subjects randomized to CZP during the Treatment Period will receive CZP 400mg Q4W from Week 12 to Week 44.

Subjects not responding to treatment during the Treatment Period will be withdrawn from the study as per Investigator's discretion and will not enter the Treatment Extension Period.

The assessments during the Treatment Extension Period are presented in [Table 5–1](#).

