19 APPENDICES

19.1 Modified New York (mNY) Classification Criteria for AS

Table 19–1: Modified New York (mNY) Classification Criteria for AS

Diagnosis
1. Clinical criteria: 
a. Low back pain and stiffness for more than 3 months which improves with exercise, but is not relieved by restb. Limitation of motion of the lumbar spine in both the sagittal and frontal planes.c. Limitation of chest expansion relative to normal values corrected for age and sex.
2. Radiologic criterion: Sacroiliitis grade ≥ 2 bilaterally or grade 3 to 4 unilaterally
Grading
1. Definite ankylosing spondylitis if the radiologic criterion is associated with at least 1 clinical criterion

AS=ankylosing spondylitis; mNY=modified New York Criteria

Note: A second grading of “probably ankylosing spondylitis” is part of the modified NY criteria, but it is not applicable for this study. It is included here for completeness. The grading will be probable ankylosing spondylitis if 3 clinical criteria are present and the radiologic criterion is present without any signs or symptoms satisfying the clinical criteria (other causes of sacroiliitis should be considered).

19.2 Markedly abnormal laboratory values**Table 19–2: Definitions of markedly abnormal hematology values**

Parameter (SI units)	Markedly Abnormal Definition	
	Low	High
Hemoglobin (g/dL)	<LLN AND >2.0 decrease from baseline	N/A
Hemoglobin (g/dL)	<8.0	N/A
Leukocytes (total x 1000)	<2.0	N/A
Lymphocytes (x 1000)	<0.5	N/A
Neutrophils (x 1000)	<1.0	N/A
Platelets (x 1000)	<50	N/A

LLN=lower limit of normal; N/A = Not Applicable; SI=standard international

Data source: modified from Appendix Rheumatology Common Toxicity Criteria v.2.0 presented in Woodworth et al, 2007

^a Withdrawal criteria for neutrophils is <0.5 (Section 6.3)**Table 19–3: Definitions of markedly abnormal biochemistry values**

Parameter (SI units)	Markedly Abnormal Definition	
	Low	High
Alkaline Phosphatase	N/A	>3 x ULN
ALT	N/A	>3 x ULN
AST	N/A	>3 x ULN
Calcium (mg/dL)	<7.0	>12.5
Creatinine (mg/dL)	N/A	>1.8 x ULN
Glucose (mg/dL)	<40	>250
Potassium (mmol/L)	<3.0	>6.4
Sodium (mmol/L)	<125	N/A
Total bilirubin	N/A	≥2 x ULN
Uric acid	N/A	≥3 x ULN

ALT=alanine aminotransferase; AST=aspartate aminotransferase; N/A=Not applicable; SI=standard international; ULN=upper limit of normal

19.3 Protocol Amendment 1

Rationale for the amendment

The purpose of this protocol amendment is the following:

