### 11.1 Extent of exposure

All IMP administration details (including date and time of administration, body site and side of administration) will be listed. Additionally, the time between each dose will be listed.

The duration of exposure to BKZ (days) will be calculated separately for the Treatment Period and the Treatment Extension Period, where the last and first dose in each equation will be the last and first dose of IMP within the Treatment Period and Treatment Extension Period respectively:

$$\text{Exposure} = (\text{Date of Last Dose} - \text{Date of First Dose}) + 140 \text{ days}$$

The duration of exposure to CZP (days) will be calculated as follows:

$$\text{Exposure} = (\text{Date of Last Dose} - \text{Date of First Dose}) + 70 \text{ days}$$

The number of days added to the BKZ and CZP exposure calculations are 5 times the half-life of each drug, respectively: 5 x 28 days for BKZ and 5 x 14 days for CZP.

Missed doses will not be accounted for in the calculation above.

The number of injections received and duration of exposure will be listed for each subject and summarized by treatment group for the Treatment Period and Treatment Extension Period separately using descriptive statistics. This summary will be repeated for subjects in the SS who were randomized in the PET-MRI/CT substudy.

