### 11.2 Adverse events

Adverse events with start date prior to the first dose of IMP are defined as pre-treatment AEs. Adverse events with a start date prior to the first dose of IMP will be defined as pre-treatment AEs. A treatment-emergent AE (TEAE) is defined as any AE with a start date/time at the time of

or after the first dose of IMP up until 140 days after the last dose of IMP. Any AE with onset later than 140 days after the last dose of IMP will not be considered as treatment-emergent and therefore will not be included in the tabulations of TEAEs. Selected summaries will be presented separately for TEAEs during the Treatment Period (any AE with a start date/time at the time or after the first dose of IMP up until the Week 12 Visit) and TEAEs during the study (as per the definition of TEAEs given above).

Where dates are missing or partially missing, AEs will be assumed to be treatment-emergent, unless there is clear evidence to suggest that the AE started prior to dosing or later than 140 days post-last dose. Handling of missing dates/times for classification of AEs as TEAEs is described in [Section 4.2.5](#).

All AEs will be recorded in the eCRF from informed consent until study completion or termination. All AEs will be coded and categorized by intensity (mild/moderate/severe) and relationship to IMP (related/not related).

An overview of the number and percentage of subjects who experience TEAEs will be presented by treatment group, based on the SS. Separate tabulations will be presented for TEAEs during the Treatment Period and TEAEs during the study and will include the number and percentage of subjects with any TEAEs, serious TEAEs, related TEAEs, discontinuation due to TEAEs, severe TEAEs, AEs leading to death and TEAEs leading to death; event counts will also be included. The summary of TEAEs during the study will be repeated for subjects in the SS who were randomized in the PET-MRI/PET-CT substudy.

In addition, the following summaries will be presented by treatment group, SOC, high level term (HLT) and PT, based on the SS:

- Incidence of TEAEs[a] [b]
- Incidence of TEAEs, stratified by overall ADA status (positive/negative) as defined in [Section 10](#)
- Incidence of serious TEAEs[a] [b]
- Incidence of non-serious TEAEs[b]
- Incidence of TEAEs by relationship
- Incidence of TEAEs by maximum relationship
- Incidence of TEAEs by maximum intensity

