### **11.3 Clinical laboratory evaluations**

Laboratory data (chemistry, hematology, and urinalysis) and changes from Baseline (if applicable) for numeric variables will be listed by treatment group and visit. Any laboratory variables that are BLQ or ALQ will be handled as described in [Section 4.2.3](#). Values outside the reference range for the numeric variables will be flagged in the listings and, in addition, will be listed separately. The reference ranges will also be reported in the listings.

Chemistry and hematology variables presented in [Table 11-1](#) will be summarized by treatment group at each visit, for both observed values and changes from Baseline. Figures of mean and mean change from Baseline will be presented by treatment for the absolute neutrophil count (ANC). All treatment groups will be overlaid on the same plot and the plot will include the error bars based on the SD (ie, mean +/-SD).

Laboratory variables will be grouped according to the laboratory function panel and categorized as normal, high or low, if applicable, based on the reference range supplied by the analytical laboratory. For selected variables that are identified in [Table 11-1](#), the change in category from Baseline will be presented in shift tables at all post-Baseline visits.

The number and percentage of subjects with treatment-emergent markedly abnormal (TEMA) values will be tabulated by treatment group and visit. Markedly abnormal laboratory values will generally be defined as those categorized as Grade 3 or Grade 4 as per the Rheumatology Common Toxicity Criteria (RCTC). Communication with the lead author of the RCTC publication has revealed that the reference ranges for absolute lymphocyte counts (ALC) are in error, therefore ALC criteria will follow the ranges defined as per the Common Terminology Criteria for Adverse Events (CTCAE) Version 4.03 (United States Department of Health and Human Services, 2010). Additional laboratory variables (not present in the RCTC publication) will also be categorized as per the CTCAE Version 4.03. The criteria for identifying TEMA values are presented in [Table 14-5](#) and [Table 14-6](#) for hematology and chemistry values respectively.

Laboratory measurements meeting the criteria for TEMA will be listed separately for hematology and chemistry. The listings will include all measurements for any variable with at least one TEMA result for each subject.

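### SAP 11.1 adds the five-half-life tail inside each study period, Table 14-5 leaves platelets from 2.0 to <20 without a grade, and the planned-injection split in SAP 7 disagrees with Table 3-2 (descriptive outputs only)

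*SAP*

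**What the plan says.** **Exposure.** SAP 11.1 sets the BKZ rule: "The duration of exposure to BKZ (days) will be calculated separately for the Treatment Period and the Treatment Extension Period". First and last dose are those within the period concerned, and the equation adds 140 days. The CZP equation adds 70 days. The SAP gives the origin of the two tails as "5 x 28 days for BKZ and 5 x 14 days for CZP". The CZP sentence does not repeat the per-period wording, but the closing paragraph of 11.1 covers both arms: "The number of injections received and duration of exposure will be listed for each subject and summarized by treatment group for the Treatment Period", and then for the Extension, separately. No rule stops the tail when the next period's dosing begins, and no whole-study exposure summary is planned. In SAP 11.2, the Treatment Period window for treatment-emergent adverse events (TEAEs) runs "at the time or after the first dose of IMP up until the Week 12 Visit".

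**Platelets.** SAP Table 14-5 gives low Grade 4 as <2.0 and low Grade 3 as 20 to <50, in 10^9/L. Protocol Table 19-2 counts every value below 50 (x 1000) as markedly abnormal.

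**Injections.** SAP 7 gives planned counts of 14 and 16 for a completer, total 30, and attaches the Treatment Period label to both. SAP 3.6 and Protocol 7.2 describe two injections at each dosing visit. The extra placebo injection in the BKZ arm is described only for Baseline, Week 2 and Week 4. SAP 3.6 says Table 3-2 shows the number of injections, but the table shows doses in mg only.

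**The concern.** A washout tail describes the time after a subject stops. Here it is also credited to subjects who receive another dose about two weeks later. The Treatment Period exposure table then reports more days than the period contains. It also shows a gap between arms that comes from the half-lives rather than from dosing. A reader who sets that table beside the Treatment Period TEAE tables is looking at two different time spans.

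In the platelet row the more severe values are the ones omitted. A count of 40 enters the table of treatment-emergent markedly abnormal (TEMA) values and a count of 10 does not.

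The injection split matters because SAP 11.1 summarises injections received by period. That summary depends on which period holds the Week 12 dose, and SAP 7 and Table 3-2 answer differently.

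**Working it through.** **Inputs**
- Treatment Period length: 12 weeks = 84 days (SAP 3.2.2).
- Dosing visits in SAP Table 3-2: Weeks 0, 2, 4, 6, 8, 10 (six visits) and Weeks 12 to 44 every four weeks (nine visits). On schedule, with the first dose as Day 0, these are Days 0 to 70 and Days 84 to 308.
- Tails: 5 x 28 = 140 and 5 x 14 = 70. Both SAP figures reproduce.

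**1. Treatment Period exposure = (last dose - first dose in the period) + tail**
- Week 12 dose in the Extension (Table 3-2): BKZ 70 + 140 = 210; CZP 70 + 70 = 140.
- Week 12 dose in the Treatment Period (the reading behind the SAP 7 split): BKZ 84 + 140 = 224; CZP 84 + 70 = 154.
- Difference between arms: 210 - 140 = 70, or 224 - 154 = 70.
- Relative to 84 days on the Table 3-2 reading: 210/84 = 2.5 and 140/84 = 1.67.
- Whole study with one tail after Week 44: BKZ 308 + 140 = 448; CZP 308 + 70 = 378.

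The documents do not settle the Week 12 boundary. Table 3-2 and Protocol 5.1.3 place that dose in the Extension. The heading of Protocol 5.1.2, SAP 4.5.2 and SAP 8.3.1 treat Week 12 as the end of the Treatment Period. The header of the protocol's schedule of assessments also appears to put the Week 12 visit under the Treatment Period, although its column spans may be broken in the text available.

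**2. Platelets against Table 14-5 as it reads**
- 1.9: Grade 4. 2.0, 10 and 19.9: no grade. 20 and 49: Grade 3. 50: no grade.
- Protocol Table 19-2 (below 50) catches all of these except 50, taking its x 1000 unit as per microlitre, which equals 10^9/L.
- The other rows of Table 14-5 for cell counts are contiguous: lymphocytes meet at 0.2, neutrophils at 0.5 and white cells at 1.0.

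**3. Planned injections = visits x injections per visit**
- Total at two per visit: 15 x 2 = 30. This reproduces SAP 7.
- Split with Table 3-2 periods: 6 x 2 = 12 and 9 x 2 = 18.
- Split with Week 12 moved to the Treatment Period: 7 x 2 = 14 and 8 x 2 = 16. At two injections per visit, only this assignment gives the SAP 7 split.
- Inference only: with a single injection at Weeks 6, 8 and 10, the total is 3 x 2 + 3 x 1 + 9 x 2 = 27, and a fully dosed completer would be listed at 27/30 = 90%.

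**The case against.** The tail is a stated definition, and 210 days follows from it openly. That is fair, and a tail as such is not the fault. What stands is that the definition is applied at the end of a period in which the subject has not stopped.

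A reader might infer that exposure is counted twice in a reported total. On Table 3-2 periods the Extension gives (308 - 84) + 140 = 364 for BKZ and 224 + 70 = 294 for CZP. The two periods would then sum to 574 and 434, against 448 and 378: an excess of 126 and 56 days. The documents do not support going that far, because the periods are summarised separately and no planned output adds them. A reader might also infer biased exposure-adjusted event rates. None are planned: the TEAE tables give subject counts, percentages and event counts. Nor does the SAP match exposure and event spans elsewhere. The whole-study TEAE window is 140 days after the last dose in both arms, while the CZP tail is 70, and the fix below leaves that difference in place.

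On platelets, a reader might infer that very low counts would go unseen. They would not. SAP 11.3 says "Values outside the reference range for the numeric variables will be flagged in the listings", and Protocol 6.3 has values meeting Table 19-2 flagged to the investigator and medical monitor. For the TEMA listing, "The listings will include all measurements for any variable with at least one TEMA result for each subject", so an ungraded count still appears there if the subject has another platelet value that does grade. The cut-off is probably a slip for <20. Even so, a program written from the table as it reads would omit the values from the TEMA table.

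On injections, a reader might infer that the total of 30 is wrong. The text does not show that: two per visit is explicit in both documents, and the 27 figure runs against it. For a completer the listed percentage depends only on the total, and SAP 7 presents no formal compliance calculation.

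**Conclusion.** The point holds as a correction to descriptive safety and dosing outputs. The primary analysis does not use any of these quantities.

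- **Exposure:** for subjects who continue into the Extension, Treatment Period exposure is overstated against an 84-day period and differs by 70 days between arms on the same dosing dates. The size is 210 and 140 days, or 224 and 154, depending on a boundary the documents leave open. It assumes on-schedule dosing and, for CZP, that the closing paragraph of SAP 11.1 extends the per-period rule to that arm.
- **Platelets:** 2.0 to <20 x 10^9/L is ungraded and lost from the TEMA table, though still listed and flagged elsewhere. This assumes the cut-off reads in the source document as it does in the text available.
- **Injections:** one label is duplicated, and 14/16 conflicts with 12/18 from Table 3-2; the total of 30 is the same either way.

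**What to change.** **Exposure (SAP 11.1).** For subjects who continue, end Treatment Period exposure at the Week 12 Visit or first Extension dose, with no tail. That gives 84 days on schedule in both arms, and 81 to 87 within the 3-day visit window. Add a whole-study exposure summary in which the tail is applied once, after the subject's last study dose: 448 days (BKZ) and 378 days (CZP) for an on-schedule completer.

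Some subjects stop in the Treatment Period, including non-responders who "will not enter the Treatment Extension Period". For them, report Treatment Period exposure only up to Week 12, show any remaining tail only in the whole-study summary, and state that the periods are not meant to add up. This truncation has a cost: a BKZ subject with one dose (tail to Day 140) and one with six doses (70 + 140 = 210) would both show 84 days. The table should therefore be read beside the number of injections received, which separates early from late withdrawals.

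**Platelets (SAP Table 14-5).** Make Grade 4 contiguous with Grade 3 (<20), after checking the boundary against the Rheumatology Common Toxicity Criteria that the table cites. Protocol Table 19-2 supports closing the gap but does not itself give a boundary at 20.

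**Injections (SAP 7).** Correct the duplicated label, state which period holds the Week 12 dose, and use that convention throughout SAP 7 and 11.1. Reconcile the stated two injections per visit with the placebo injection described only for Weeks 0, 2 and 4, across Protocol 7.2 and SAP 3.6, Table 3-2 and Section 7. The sponsor must say which description applies.

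**Cost.** SAP text edits, one source check and one added summary table. No new data are needed.

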### 11.2 Adverse events

Adverse events with start date prior to the first dose of IMP are defined as pre-treatment AEs. Adverse events with a start date prior to the first dose of IMP will be defined as pre-treatment AEs. A treatment-emergent AE (TEAE) is defined as any AE with a start date/time at the time of

or after the first dose of IMP up until 140 days after the last dose of IMP. Any AE with onset later than 140 days after the last dose of IMP will not be considered as treatment-emergent and therefore will not be included in the tabulations of TEAEs. Selected summaries will be presented separately for TEAEs during the Treatment Period (any AE with a start date/time at the time or after the first dose of IMP up until the Week 12 Visit) and TEAEs during the study (as per the definition of TEAEs given above).

Where dates are missing or partially missing, AEs will be assumed to be treatment-emergent, unless there is clear evidence to suggest that the AE started prior to dosing or later than 140 days post-last dose. Handling of missing dates/times for classification of AEs as TEAEs is described in [Section 4.2.5](#).

All AEs will be recorded in the eCRF from informed consent until study completion or termination. All AEs will be coded and categorized by intensity (mild/moderate/severe) and relationship to IMP (related/not related).

An overview of the number and percentage of subjects who experience TEAEs will be presented by treatment group, based on the SS. Separate tabulations will be presented for TEAEs during the Treatment Period and TEAEs during the study and will include the number and percentage of subjects with any TEAEs, serious TEAEs, related TEAEs, discontinuation due to TEAEs, severe TEAEs, AEs leading to death and TEAEs leading to death; event counts will also be included. The summary of TEAEs during the study will be repeated for subjects in the SS who were randomized in the PET-MRI/PET-CT substudy.

In addition, the following summaries will be presented by treatment group, SOC, high level term (HLT) and PT, based on the SS:

- Incidence of TEAEs[a] [b]
- Incidence of TEAEs, stratified by overall ADA status (positive/negative) as defined in [Section 10](#)
- Incidence of serious TEAEs[a] [b]
- Incidence of non-serious TEAEs[b]
- Incidence of TEAEs by relationship
- Incidence of TEAEs by maximum relationship
- Incidence of TEAEs by maximum intensity
- Incidence of fatal TEAEs by relationship
- Incidence of non-serious TEAEs by relationship
- Incidence of serious TEAEs by relationship
- Incidence of non-serious TEAEs above threshold of 5% of subjects
- Incidence of non-serious TEAEs above threshold of 5% of subjects by relationship
- Incidence of TEAEs by SOC and PT (including the number and percentage of subjects and individual subject numbers for each PT stratified by intensity, relationship and seriousness)

[a] These summaries will be presented separately for TEAEs during the Treatment Period and TEAEs during the study.

[b] These summaries will be repeated for subjects in the SS who were randomized in the PET-MRI/PET-CT substudy and will be based on TEAEs during the study

In addition, separate summaries by treatment group, SOC, HLT and PT will be included for the following AEs for special monitoring (AESM):

- Major cardiovascular events
- Serious infections, including opportunistic infections and tuberculosis (TB)
- Malignancies including lymphoma
- Cytopenias
- Neuropsychiatric events
- Inflammatory bowel disease
- Anaphylactic reaction (hypersensitivity and anaphylactic reactions)
- Hepatic events and drug-induced liver injury

The criteria for identifying and additional criteria for reporting AESM are provided in [Section 14.5](#).

All summary tables (including those for AESM) will contain the number and percentage of subjects and the number of events where applicable. A subject who has multiple events in the same SOC, HLT and PT will be counted only once in the subjects counts but all events will be included.

In summaries including relationship to IMP, the following relationship categories will be included:

- Related
- Not related

Subjects who experience the same event multiple times will be included in the most related category for tabulations by maximum relationship. Events with missing relationship will be considered as 'Related' for summary purposes but shown as missing in the data listings.

In summaries including intensity, the following categories will be summarized:

- Mild
- Moderate
- Severe

Subjects who experience the same event multiple times will be included in the most severe category for tabulations by maximum intensity. Events with missing intensity will be considered as 'Severe' for summary purposes. All data will be presented as recorded in the database for the listings.

Adverse event summaries will be ordered by alphabetical SOC, alphabetical HLT within SOC and decreasing frequency of PT in the 'BKZ' column for tables including event counts. For tables including only number and percentage of subjects, summaries will be ordered by alphabetical SOC, alphabetical HLT within SOC and decreasing incidence of PT within HLT and SOC in the 'BKZ' column.

Listings will be presented by treatment group and subject for all AEs, serious adverse events (SAEs), AEs leading to death and AEs leading to withdrawal. Listings will include the onset date/time and outcome date/time of the event (including relative days), the AE duration (derived), days since first dose of IMP, days since most recent dose of IMP, pattern of event, intensity, relationship, action taken and outcome. In addition, the listing will flag AEs that led to discontinuation, TEAEs, AESM and SAEs. All AE listings will be based on all subjects screened.

A glossary of all TEAE terms will be provided including the SOC, HLT, PT and reported term.

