## 2.3 Study design and conduct

AS0013 is a multicenter, randomized, subject-blind and investigator-blind, parallel-group study to evaluate the efficacy and safety of BKZ compared to CZP in adult subjects with active adult-onset AS.

It is planned that at least 60 subjects will be randomized to 1 of 2 treatment arms in a 2:1 ratio and will receive either BKZ or CZP up to Week 44 (final dose of investigational medicinal product [IMP]).

The study will include a Screening Period of 2 to 4 weeks, a 12-week Treatment Period, a 36-week Treatment Extension Period, and a 20-week Safety Follow-up (SFU) Period (starting after the final dose of IMP). Therefore, the maximum duration of the study will be 68 weeks.

At the start of the Treatment Period, eligible subjects will be randomized in a 2:1 ratio to receive the following blinded study treatments:

- BKZ 160mg sc Q2W from Week 0 through Week 10. In addition, subjects will receive 1 placebo injection at Baseline (Visit 2), Week 2 (Visit 3), and Week 4 (Visit 3) in order to maintain the blind versus the CZP loading dose at these visits.
- CZP 400mg sc Q2W at Weeks 0, 2, and 4 (loading dose) followed by CZP 200mg sc Q2W at Weeks 6 to 10.

After completing the 12-week Treatment Period, subjects will enter a 36-week Treatment Extension Period and will receive the following treatments:

- Subjects randomized to BKZ during the Treatment Period will receive BKZ 320mg sc every 4 weeks (Q4W) from Week 12 to Week 44.
- Subjects randomized to CZP during the Treatment Period will receive CZP 400mg Q4W from Week 12 to Week 44.

Subjects not responding to treatment during the Treatment Period will be withdrawn from the study as per Investigator's discretion and will not enter the Treatment Extension Period.

In a substudy of AS0013, a PET-MRI or PET-CT scan of the entire spine will be performed at selected sites in approximately 25 subjects at Screening and during the study at Week 12 and Week 48 or Early Withdrawal Visit if PET positive lesions were observed in the previous scan.

All subjects who complete the study or who discontinue from the study early, including those withdrawn from the IMP treatment, will have a SFU Visit at 20 weeks after their final dose of IMP.

Three unblinded interim analyses will be conducted:

- Interim Analysis 1 (IA1): when approximately 45 subjects have completed the Week 4 visit during the Treatment Period.

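### Whole-study TEAE tables make no allowance for time at risk, so they could mislead if withdrawal for non-response at Week 12 differs between arms

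*SAP*

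**What the plan says.** SAP 11.2 counts an event as treatment-emergent if it starts at "or after the first dose of IMP up until 140 days after the last dose of IMP", in both arms alike. For the overview it states: "Separate tabulations will be presented for TEAEs during the Treatment Period and TEAEs during the study". A footnote gives the same split to the all-TEAE and serious-TEAE tables. The remaining tables, including those for adverse events for special monitoring (AESM), are not split by period.

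Each summary table holds the number and percentage of subjects and, where applicable, the number of events. Under SAP 3.1 the default denominator is every subject in the analysis set and arm. Neither document plans an incidence or event rate per subject-time, or a time-to-event summary of adverse events.

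Protocol 5.1.3 states: "Subjects not responding to treatment during the Treatment Period will be withdrawn from the study as per" the Investigator's discretion. SAP 2.3 repeats that they "will be withdrawn from the study as per Investigator's discretion and will not enter the Treatment Extension Period". Dosing in the Treatment Period is "BKZ 160mg sc Q2W from Week 0 through Week 10", with certolizumab pegol (CZP) also dosed up to Week 10. In the extension, bimekizumab (BKZ) subjects "will receive BKZ 320mg sc every 4 weeks (Q4W) from Week 12 to Week 44" and CZP subjects "will receive CZP 400mg Q4W from Week 12 to Week 44".

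**The concern.** A percentage of subjects with an event compares arms fairly only if the arms are followed for similar lengths of time. Here follow-up depends on whether a subject enters the extension, and that depends partly on efficacy. If one drug leaves more non-responders at Week 12, that arm accrues less time in the TEAE window and shows fewer subjects with events and fewer events, even when the underlying rates are equal.

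At stake is how the whole-study tables are read. Safety and tolerability of BKZ is the secondary objective, and safety during the extension is an exploratory one. These tables are the only planned TEAE summaries that cover the 36 extension weeks, and for AESM they are the only ones at all.

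**Working it through.** **Time at risk.** Inputs: last dose at Week 44 (completer) or Week 10 (extension not entered), from SAP 2.3; 140 days = 20 weeks, from SAP 11.2.

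- Completer: 44 + 20 = 64 weeks. This reproduces the Week 64 last visit in SAP 5.1, and 4 + 44 + 20 = 68 weeks reproduces the stated maximum duration.
- Withdrawn at Week 12 without the Week 12 dose: 10 + 20 = 30 weeks, and 30/64 = 46.9%. If the Week 12 dose were given first: 12 + 20 = 32 weeks, or 50%.

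**Effect on crude percentages.** The documents give neither withdrawal rates nor event rates, so both are assumed here. Let p64 be the 64-week risk, the same in both arms, with constant hazard h = −ln(1 − p64)/64. Then p30 = 1 − (1 − p64)^(30/64). If a share w leaves at Week 12, the crude percentage is (1 − w)·p64 + w·p30, and mean time at risk is (1 − w)·64 + w·30.

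For p64 = 50%, p30 = 1 − 0.5^0.46875 = 27.7%. With w = 10%: 0.9 × 50 + 0.1 × 27.7 = 47.8%. With w = 30%: 0.7 × 50 + 0.3 × 27.7 = 43.3%.

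| Leaving at Week 12 | Mean weeks at risk | p64 = 10% | p64 = 50% | p64 = 80% |
|---|---|---|---|---|
| 5% v 20% | 62.3 v 57.2 | 9.7 v 9.0 (gap 0.8) | 48.9 v 45.5 (3.3) | 78.6 v 74.6 (4.1) |
| 10% v 30% | 60.6 v 53.8 | 9.5 v 8.4 (1.0) | 47.8 v 43.3 (4.5) | 77.3 v 71.9 (5.4) |
| 10% v 40% | 60.6 v 50.4 | 9.5 v 7.9 (1.6) | 47.8 v 41.1 (6.7) | 77.3 v 69.2 (8.1) |

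Gaps are in percentage points, taken before rounding. With equal withdrawal the gap is zero. Event counts per subject shrink with mean time: 53.8/60.6 = 0.888 (11% fewer) and 50.4/60.6 = 0.832 (17% fewer).

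**Is 10% v 30% plausible?** The sample-size section assumes mean ASDAS changes of −1.78 (CZP) and −2.67 (BKZ) with SD 1.17, and SAP 8.2.1.1 defines clinically important improvement as at least 1.1 units. Under normality, the share missing it is 1 − Φ((1.78 − 1.1)/1.17) = 28% for CZP and 1 − Φ((2.67 − 1.1)/1.17) = 9% for BKZ. Neither document defines non-response this way, so this shows only that the scenario is not extreme. Under the sponsor's own hypothesis, BKZ would be the arm that looks worse.

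**A rate over time at risk.** Under a constant hazard, expected time to first event or end of window is the crude proportion divided by h. For p64 = 50%, h = 0.6931/64 = 0.01083 per week. With 10% leaving, 0.478/0.01083 = 44.1 weeks; with 30% leaving, 0.433/0.01083 = 40.0 weeks. Events over time return 0.01083 per week in both arms, or 56.5 per 100 subject-years (52.18 weeks per year).

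**Can the planned exposure table supply the denominator?** No. SAP 11.1 adds 140 days for BKZ and 70 days for CZP, while the TEAE window adds 140 days for both. It also computes BKZ exposure separately by period. A BKZ completer sums to (10 + 20) + (32 + 20) = 82 weeks. A CZP completer treated the same way sums to (10 + 10) + (32 + 10) = 62. Both are at risk for 64 weeks, and 82/62 = 1.32.

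**The case against.** Much of the case on the other side stands.

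- A reader might infer that the tables hold only percentages. They do not: event counts are given as well. But counts without a time denominator carry the same distortion.
- A reader might infer that every non-responder must leave at Week 12. The documents leave this to the Investigator, define no response threshold and state no rate.
- Unequal follow-up would not be invisible. Disposition is summarized for the Treatment Period and the extension with reasons for discontinuation, exposure is tabulated, and AE listings show days since first and most recent dose.
- A comparison over a common window exists. The Treatment Period overview, all-TEAE and serious-TEAE tables end at the Week 12 Visit, before the non-responder rule can act. They do not cover the extension or AESM.
- Safety is descriptive, and the secondary objective names BKZ without an explicit comparison with CZP.
- The effect is small against chance. With 40 v 20 subjects, 47.8% v 43.3% has standard error √(0.478 × 0.522/40 + 0.433 × 0.567/20) = 13.6 points, so a 95% half-width of about 27 points; with 48 v 24 it is about 24. A gap of 4.5 points is about a third of a standard error.
- A rate restores equality fully only under a constant hazard. A Week 12 leaver spends 20 of 30 window weeks after the last dose, a completer 20 of 64. If hazard falls off treatment, some dilution remains, though less than in the crude percentage.

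None of this supplies a measure of time at risk for the whole-study or AESM tables.

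**Conclusion.** The gap in the plan is real and its consequence is conditional. The whole-study TEAE tables take no account of time at risk, although the design lets that time fall from 64 to about 30 weeks for subjects withdrawn at Week 12. If withdrawal differs between arms, the arm losing more would show somewhat fewer events at equal true rates: about 1 to 4 points at 5% v 20% leaving, and 4.5 points at 10% v 30% with a 64-week risk of 50%. These figures rest on assumed withdrawal shares, a constant hazard common to both arms, and no other loss to follow-up.

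A reader might infer that the long-term safety comparison is certainly biased, or that the arm losing more subjects must look safer. The documents do not support that. They do not say that withdrawal will differ, and an arm losing subjects because of adverse events need not look safer. This is a worthwhile reporting improvement for a descriptive safety section, not a flaw that invalidates it.

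**What to change.** In SAP 11.2, keep n (%) and event counts. Add subjects with a first event per 100 subject-years at risk, with 95% CI, to:

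- the whole-study overview, all-TEAE and serious-TEAE tables;
- the overall incidence row of each AESM table.

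Define time at risk as first dose to the earliest of first event, last contact, and last dose plus 140 days, with the same rule in both arms. State that the SAP 11.1 exposure is not used for this purpose.

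The cost is small. Dates of first and last dose, final contact and event onset are already collected for the listings. It needs a new derived variable distinct from exposure, a sentence in the CSR on the constant-rate assumption, and acceptance that intervals for rare AESM will be wide, particularly with some 20 to 24 CZP subjects. No clinical rule changes.
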